12.7.2 Secondary Infection endpoints

Superficial incisional/wound infections, deep incisional wound infections, and organ/space infections, and ventilator associated pneumonia during the 14 days after study product administration by individual patient, as well as the allocated group and the time of events will be

listed. Also, the above infection endpoints will be summarized as patient counts and percentages by allocated group in modified ITT Population.

12.7.3 Sequential Organ Failure Assessment (SOFA) score

Non-pulmonary Sequential Organ Failure Assessment (SOFA) score will be calculated at baseline, 3, and 7 days, as described in **Section 8.3**.

The non-pulmonary SOFA scores at each timepoint, as well as the score changes from the baseline, will be summarized by allocated group, as mean and standard deviation.

Furthermore, non-pulmonary SOFA score, will be compared between treatment groups using a linear mix-effects regression model, which is similar to the analyses of the primary endpoint of oxygenation index.

12.7.4 In-hospital mortality at 14, 28 and 60 days

In-hospital mortality at 60 days is defined as all death following the initiation of study product administration in any health care facility prior to discharge “home” until study day 60. Study subjects still in a health care facility at study day 61 are considered alive for this endpoint. This definition will also applied to in-hospital mortality at 14 days and 28 days.

At interim analyses hospital mortality to day 60 will be estimated using the Kaplan Meier estimate with patients who are discharged home considered as censored at day 61. At the final analyses where 60 day mortality will be known for everyone the binomial estimate will be used. In-hospital mortality will be summarized as patient counts and percentages by allocated groups, and compared by Pearson’s chi-square tests or Fisher exact tests, as appropriate.

At the final report, in hospital mortality at 28 days and 60 days will also be analyzed with a unadjusted Cox proportional hazard model and reported as hazard ratios (HRs) with 95% confidence intervals. Furthermore, a multivariate Cox proportional hazard model will be applied, by including the stratification variables ($\text{PaO}_2/\text{FiO}_2 < 150 \text{ mmHg}$ or $\geq 150 \text{ mmHg}$; trauma vs. non-trauma), and any baseline parameters that suggests the evidence of randomization imbalance between two groups.

In addition, as described in Section 7.1.2, we will use the levels of the baseline plasma biomarkers (IL-8, Protein C, and serum bicarbonate \pm vasopressor use at randomization) to classify patients as hyper- or hyper-inflammatory subphenotypes. Using latent class analysis (LCA), we will test the association between hyper-inflammatory group and an increased higher hospital mortality at 28 and 60 days in the modified ITT population.

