9.12 Day 60 Measurements

Vital status and the need for dialysis will be collected at day 60 after study product infusion. If patients are discharged from the hospital prior to day 60, we will collect this data through telephone interviews with care-givers at the outside facility, or family members, or the patient.

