Ventilator history and ICU history [@]																			X	
Need for, timing and duration of dialysis																		X	X	
Vital Status §																		X	X	
Ordinal Scale for Clinical Improvement (OSCI)	X														X			X	X	
Incidence of barotrauma		X						X	X	X				X						

X=Required; A=When available; ~Data gathered on days 0-14 or until d/c from study hospital; \$=Data recorded every 15 minutes for at least two hours during "stable baseline" period and until the initiation of study product infusion, every 15 minutes for the duration of the infusion and every hour until 6 hours, then 12, 24 and 48 hour from the initiation of study product infusion; #Data recorded every 15 minutes for at least two hours during "stable baseline" period and until the initiation of study product infusion, every 15 minutes for the duration of the infusion and every hour until 6 hours, then 12, 18, 24 and 36 hour from the initiation of study drug infusion, then day 2, 3, 4, 5, 6, and 7; &=ABG mandatory at the following timepoints: within 6 hours of randomization, prior to the start of the infusion (within 90 minutes of starting the baseline stability period); within 15 minutes of the end of MSC infusion (~1 hour); after the initiation of the study product infusion, ABGs will also be REQUIRED at 6, 12, 18, 24, 30, 36 hours (+/- 1 hour for all timepoints), day 2 (48 hours +/- 4 hours), 3 and 7 (anytime) if patient still has arterial line after study product infusion; €=Record only one episode during the 14 day period after study product infusion, no need for further assessment once first diagnosis is confirmed; %=Labs not available in the 24 hours before randomization must be obtained; ¶=Data gathered for first 14 days during current hospital admission; @=Measure at day 28. The 28-day follow up will be a telephone interview with structured survey if patient discharged prior to day 28; §=Measure at day 28, day 60, hospital discharge alive, and 6 months; the 6 month follow up will be a telephone interview with structured survey. B=Patient must achieve a stable baseline for ≥ 2 hours and the administration of study product must be initiated within 14 days of initial ICU admission; C=Record available clinical data within 24 hours prior to study randomization; D=Record ECHO if available. If more than one ECHO data available, select the data closest to randomization; E=Record clinically available worst SBP, PaO2/FiO2, SpO2/FiO2, creatinine, platelets, bilirubin, and vasoressor use; F=Measured on day 0, 1, 2, 3, 7 when patient is on assisted breathing; G=Record clinically available creatinine in the 96 hours prior to randomization, the worst creatinine of the day from day 1-14, the date and value of the highest creatinine between days 15-28 and the lowest value during the entire hospitalization obtained off dialysis; H=Data required prior to randomization, day 3 (+/-1 day) and day 7 (+/-1 day); J=Mandatory at the following timepoints: pre-randomization, pre-infusion, day 1, 2, 3, 7, 14 and the date of hospital discharge; K=Record outpatient medication (anticoagulants/antiplatelets/antifibrinolytic) within 7 days prior to current hospital admission; record the following medication and procedures (glucocorticoids, NMBD, inhaled vasodilators, prone positioning, recruitment maneuvers, ECMO) prior to randomization and on day 1-7; and inpatient trauma specific medications for first 14 days during current hospital admission; M= Record any co-enrollment of clinical trials and COVID-19 related therapies within 7 days prior to current hospitalization until hospital discharge; N=Blood specimens are required before the study product infusion, at 6, 12, 24 hours (+/- 1 hour), and 2 (48 hours +/- 4 hours), 3 days (anytime) after the initiation of the study product infusion. O=Urine specimens are required before the study product infusion, at 24 hours and 2 days (48 hours +/- 4 hours) after the initiation of the study product infusion.

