8.9 Ventilator Free Days

Ventilator Free Days (VFDs) to day 28 are defined as the number of days from the time of initiating unassisted breathing to day 28 after study product administration, assuming survival for at least

two consecutive calendar days after initiating unassisted breathing and continued unassisted breathing to day 28. If a patient returns to assisted breathing and subsequently achieves unassisted breathing to day 28, VFDs will be counted from the end of the last period of assisted breathing to day 28. A period of assisted breathing lasting less than 24 hours and for the purpose of a surgical procedure will not count against the calculation of VFDs. If a patient was receiving assisted breathing at day 27 or dies prior to day 28, VFDs will be zero. Patients transferred to another hospital or other health care facility will be followed to day 28 to assess this endpoint. Similarly, we will use the same methodology to calculate ventilator free days over 7 and 14 days.

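### Deaths after discharge home count as survival in the mortality endpoint, although vital status is collected at days 28 and 60 and no all-cause comparison is planned

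*SAP*

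**What the plan says.** SAP 12.7.4 counts as an event "all death following the initiation of study product administration in any health care facility prior to discharge" home, up to day 60, and treats patients still in a facility on day 61 as alive. It extends the rule to the earlier time points: "This definition will also applied to in-hospital mortality at 14 days and 28 days". For the interim it specifies a "Kaplan Meier estimate with patients who are discharged home considered as censored at day 61", which keeps them event-free through the whole window. For the final report it states: "At the final analyses where 60 day mortality will be known for everyone the binomial estimate will be used". It also plans unadjusted and multivariable Cox models for in-hospital mortality at 28 and 60 days, without saying how discharge home is handled in them.

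Follow-up does not stop at discharge. Protocol 9.12 states: "Vital status and the need for dialysis will be collected at day 60 after study product infusion". For patients who have left hospital it adds: "we will collect this data through telephone interviews with care-givers at the outside facility, or family members, or the patient". The vital status footnote in Protocol Appendix A reads "Measure at day 28, day 60, hospital discharge alive, and 6 months". Vital status at 60 days is the first endpoint determination in both documents (Protocol 10.5, SAP 6.1.5).

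Other endpoints count death wherever it occurs. SAP 8.9 says that if a patient "dies prior to day 28, VFDs will be zero". SAP 8.7 scores death as 8 on the ordinal scale for clinical improvement (OSCI), for all patients, by chart or by telephone after discharge. The subphenotype interaction in Protocol 6.2.1 and SAP 7.2.1 uses 28-day mortality with no hospital limit, whereas SAP 12.7.4 relates subphenotype to hospital mortality.

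**The concern.** The plan gathers the data for a complete mortality comparison and then analyses a restricted one. A death at home is known to the trial but does not enter the mortality endpoint, while the same death enters ventilator-free days (VFDs) and the OSCI. Two tables of one report could then show different numbers of deaths by day 28.

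The Cox model adds an ambiguity. If discharge home censors a patient, those well enough to leave drop out of the risk set, and that censoring is informative. If they are carried to day 61 as in the interim rule, home deaths become survival. The SAP does not say which applies.

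Complete counts matter here because phase 2a had 28-day mortality of 30% on hMSCs against 15% on placebo (Protocol 3.6). That difference was not significant (p = 0.24) and baseline severity was imbalanced. It is a reason to count every death, not evidence of harm.

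**Working it through.** The plan gives no expected rate, event count or power for mortality, so there is no stated figure to reproduce. The check is of the rules, followed by an illustration of size.

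**1. Two hypothetical home deaths under each rule**

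| Rule | Death at home, day 20 | Death at home, day 45 |
|---|---|---|
| In-hospital mortality, day 28 (SAP 12.7.4) | not a death | not a death; alive on day 28 under any rule |
| In-hospital mortality, day 60 (SAP 12.7.4) | not a death | not a death |
| VFDs to day 28 (SAP 8.9) | 0 | not affected |
| OSCI, day 28 (SAP 8.7) | 8 | not affected |
| Vital status, day 28 (Protocol Appendix A) | dead | alive |
| Vital status, day 60 (Protocol 9.12) | dead | dead |

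The clash with VFDs and the OSCI is therefore limited to deaths up to day 28. After that, in-hospital mortality disagrees only with the collected vital status.

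**2. Weight of one death.** With 60 per arm (SAP 10), 1/60 = 1.7 percentage points. Mortality of 25–40% (Protocol 3.7.1) in 120 patients gives 30–48 deaths in total.

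**3. How many could be missed.** The documents give no rate of death after discharge home, so this part is assumption. Let m be mortality in a facility, s the share of survivors sent home by day 60, and h the share of those who die there. Uncounted deaths per arm = 60 × (1 − m) × s × h. The range for m runs from the phase 2a placebo rate to the top of the Protocol 3.7.1 range; s and h are assumed.

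- Low (m = 0.40, s = 0.50, h = 0.02): 60 × 0.60 × 0.50 × 0.02 = 0.4 deaths, or 0.6 points.
- Middle (m = 0.25, s = 0.70, h = 0.05): 60 × 0.75 × 0.70 × 0.05 = 1.6 deaths, or 2.6 points; 25.0% becomes 27.6%.
- High (m = 0.15, s = 1.00, h = 0.10): 60 × 0.85 × 1.00 × 0.10 = 5.1 deaths, or 8.5 points.

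The high case needs every survivor to go home and one in ten of them to die there, so it is an outer bound.

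**4. Sensitivity of a test.** Carrying the phase 2a percentages to 60 per arm gives 9/60 v 18/60, Pearson chi-square p = 0.049. One uncounted home death in the lower arm gives 10/60 v 18/60, p = 0.084. These counts are chosen for illustration, and a home death in the other arm would move the result the other way.

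**5. Against sampling error.** The 95% half-width of a risk difference is 1.96 × √(2p(1 − p)/60): 15.5 points at p = 0.25 and 17.5 points at p = 0.40. A shift of 1.7 points is well inside that.

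**The case against.** The strongest reply is that nothing is hidden. Both documents name the endpoint in-hospital mortality and SAP 12.7.4 defines it exactly. Deaths after transfer to another care facility still count; only deaths after going home are lost. VFDs, the OSCI and in-hospital mortality are different endpoints with their own rules, and none claims to report the same count. All of this stands. It makes the definition a disclosed choice of estimand, and a reader who inferred a mislabelled endpoint would be wrong.

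A reader might also infer that home deaths escape safety review. They do not up to day 28: Protocol 12.1 makes any death in the study period reportable and has discharged patients contacted after day 28.

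A reader might infer a bias between arms, or differences in discharge practice across the seven sites. The documents support neither. The trial is blinded with 1:1 allocation, study personnel do not decide on discharge (Protocol 9.11), and nothing is said about how sites differ.

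Mortality is one of the secondary endpoints that SAP 12.5 calls supportive and exploratory, so no decision turns on crossing 0.05. Vital status may also be incomplete despite the SAP's statement about 60-day mortality, because a patient who withdraws gets a survival call only on agreement (Protocol 7.7.2, SAP 9). Vital status is not scheduled at day 14, and no listed item is the date of a death after discharge.

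These points limit the size of the problem and shape the remedy. They do not explain why vital status is collected to day 60 with no planned all-cause comparison between arms.

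**Conclusion.** The point holds as a gap in the analysis plan. SAP 12.7.4 scores a death after discharge home as survival at all three time points, and no all-cause comparison fills the gap. Up to day 28 such a death is counted by the OSCI and, if before day 28, by VFDs, so two 28-day death counts are possible. From day 29 to day 60 the disagreement is with vital status alone; a conflict of VFDs or the OSCI with 60-day mortality should not be inferred, because both stop at day 28.

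Each affected death is worth 1.7 points in its arm. The number of such deaths is unknown. The range of 0.4 to 5.1 per arm rests wholly on assumed discharge and home-death rates, and the low end is more plausible than the high end. The case for change is that the complete comparison is nearly free, not that a large error is expected. Nothing here calls for a stratified Cox model, since the multivariable model already includes both randomization strata.

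**What to change.** In SAP 12.7.4:

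- Add a between-arm comparison of all-cause mortality at days 28 and 60 from the start of infusion, using the collected vital status, and report it beside in-hospital mortality. Take day 14 from the OSCI and adverse event follow-up.
- Record the date of any death after discharge.
- Run the Cox model on all-cause death, censoring only at last known vital status or the end of the window (day 28 or day 60). Discharge home should not censor.
- Censor patients who withdrew without a survival call at last contact, and report how many there are in each arm.
- Use the all-cause definition for the 28-day mortality interaction with subphenotype.

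The cost is SAP wording, matching wording in Protocol 6.2.1, and one date item in telephone interviews already planned. In-hospital mortality stays as defined. Reported all-cause mortality may be slightly higher than the in-hospital figure.

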12.7.5 Additional Prognostic value of neutrophil-to-lymphocyte ratio

Neutrophil-to-lymphocyte ratios (NLR) will be calculated at baseline, days 1, 2, 3, 7, and summarized in modified ITT populations and in patients with confirmed COVID-19, stratified by the allocated groups. If NLR is skewed, log transformation will be applied to create normally

distributed data. The predictive values of NLR at baseline for poor clinical outcomes, including hospital mortality by day 28 and day 60, will be assessed using the receiver operating characteristic (ROC) curve and the optimal cutoff values of NLR will be determined using Youden's index.

To further evaluate the additional prognostic values of NLR on hospital mortality by day 28 and day 60, we will perform multivariate logistic Cox regression models which includes: baseline NLR value, $\text{PaO}_2/\text{FiO}_2 < 150$ mmHg or ≥ 150 mmHg, trauma vs. non-trauma, study product assignment and any baseline parameters that suggests the evidence of randomization imbalance between two treatment groups. This model will also be further conducted in the subgroup of patients with COVID-19 as a cause of ARDS, which is adjudicated by the study physicians.

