8.2 Acute Physiology, Age, Chronic Health Evaluation (APACHE) III

APACHE III is a validated scoring system to provide risk estimates for hospital mortality for individual ICU patients.(18) It is comprised of the sum of three components: an acute physiology score, an age score, and a chronic health problem score. Scores range from 0 to 299 (physiology, 0 to 252; chronic health evaluation, 0 to 23; age, 0 to 24, with higher values representing a worse prognosis. The worst values within 24 hours prior to randomization will be calculated for APACHE III score.

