12.5 General Methodology

Study Investigators, Study Coordinators, Data Manager and Statistician will be blinded to treatment assignment (randomization assignment will be coded as A group vs. B group) during the study prior to data lock.

Parameters ascribed to the safety and efficacy of patients will be summarized by modified ITT population defined in Section 11.

Continuous variables will be summarized using tables of descriptive statistics: number of patients with recorded observations, mean, standard deviation, median, minimum, maximum and interquartile range (IQR). Comparison of continuous parameters between two groups will be performed using T-test or Wilcoxon-Mann-Whitney test, as appropriate. Categorical variables will be summarized using counts and percentages, and compared between two groups using Pearson's chi-square or Fisher exact test, as appropriate. Based on the data shown in our previous Phase 2a

study, biomarker data will be summarized with descriptive statistics described above on original scale and log-transformed scale.

All statistical tests will be two-sided and will be performed at the 5% level of significance, unless otherwise stated. P-values will be rounded to three decimal places. P-values less than 0.001 will be reported as < 0.001 in tables. In bivariate analyses, P-values will not be adjusted for the comparisons of repeated outcomes between treatment allocations at multiple timepoints. Additional ad-hoc analyses may be conducted as deemed suitable.

As there is a single primary endpoint, and the secondary endpoints are to be used only in providing additional supportive exploratory information, there will be no adjustment for multiple testing.

All outputs will be produced using SAS and STATA (most up to date version available).

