12.7.9 Additional prognostic value of baseline fibrinogen

Baseline fibrinogen will be summarized by median with interquartile range. If it is skewed, log transformation will be applied to create normally distributed data. The predictive values of baseline fibrinogen for poor clinical outcomes, including hospital mortality by day 28 and day 60, will be assessed using the receiver operating characteristic (ROC) curve and the optimal cutoff values of fibrinogen will be determined using Youden's index.

To further evaluate the additional prognostic values of baseline fibrinogen on hospital mortality by day 28 and day 60, we will perform multivariate logistic Cox regression models which includes: baseline fibrinogen value, $\text{PaO}_2/\text{FiO}_2 < 150$ mmHg or ≥ 150 mmHg, study product assignment and any baseline parameters that suggests the evidence of randomization imbalance between two treatment groups. This model will also be performed in the subgroup of patients with COVID-19.

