12.8 Adjustments for Stratification and SARS-CoV-2 Infection

Analyses of the outcomes will be adjusted for stratification variables (PaO₂/FiO₂ ratio [<150 mmHg or ≥ 150 mmHg] and trauma vs. non-trauma), APACHE III scores at baseline, and baseline measure, where P-value < 0.20 between treatment group.

To better understand the hMSC effects in patient with COVID-19 disease, the primary and secondary endpoints specified in Section 12.6 and 12.7 will also be summarized and conducted in separate linear mixed-effects regression models, in a fashion parallel to the analyses of the above main primary endpoint models, stratified or adjusted by the following binary variables of interest prior to randomization:

- SARS-CoV-2 infection status obtained from medical chart: yes or no
- COVID-19 as a cause of ARDS which is adjudicated by the study physicians: yes or no
- Viral antigen levels measured by NIH lab (PI: [name]): the value will be categorized by greater or less than median value
- Dexamethasone (or equivalent steroid therapy): yes or no
- Other immunomodulatory agents: yes or no
- Anticoagulation and antiplatelet treatments: yes or no
- MSC viability at the time of administration

Furthermore, the primary and secondary endpoints will be analyzed by latent class analysis (LCA) subphenotype using the same procedures described in previous studies (23-26) and adjusted for SARS-CoV-2 infection. In addition, we will test for an interaction between MSC therapy and the subphenotypes for the clinical outcomes.

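### The NLR and fibrinogen models in SAP 12.7.5 and 12.7.9 pick extra covariates by imbalance between arms, and the SAP leaves unclear whether APACHE III is always included

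*SAP*

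**What the plan says.** The added prognostic value of NLR and of baseline fibrinogen are listed secondary endpoints (Protocol 6.2.1, SAP 7.2.1). For hospital mortality by day 28 and day 60, the SAP plans two steps for each marker.

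- **ROC step.** For NLR, "the optimal cutoff values of NLR will be determined using Youden's index"; 12.7.9 does the same for fibrinogen. No covariates and no validation or optimism correction are described.
- **Regression step.** The NLR model (12.7.5) contains baseline NLR, P/F below or at least 150 mmHg, trauma status, and "study product assignment and any baseline parameters that suggests the evidence of randomization imbalance between two treatment groups". For fibrinogen (12.7.9), "we will perform multivariate logistic Cox regression models which includes: baseline fibrinogen value", followed by the P/F stratum, treatment and the same imbalance rule. Trauma is not listed there, although it is a randomization stratum (12.2). Both regressions are repeated in patients with COVID-19.

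Neither section names APACHE III, defines a reference model, or says what counts as imbalance. Elsewhere, SAP 8.2 calls APACHE III a "validated scoring system to provide risk estimates for hospital mortality for individual ICU patients". SAP 12.8 sets a general rule: "Analyses of the outcomes will be adjusted for stratification variables", then "APACHE III scores at baseline, and baseline measure, where P-value < 0.20 between treatment group".

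**The concern.** Added prognostic value means that a marker predicts death beyond what is already known about the patient. The covariates that matter are therefore those that predict death and may be related to the marker. Randomization makes imbalance between arms a chance event, unconnected to either property. A strong predictor of death is usually balanced and so would usually be left out. A variable with no bearing on death can be let in.

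If APACHE III is left out, an NLR that merely tracks severity of illness can show a significant coefficient and be written up as adding prognostic information. Two analysts following the same SAP could also fit different models, because 12.7.5, 12.7.9 and 12.8 give different covariate lists and the model is labelled both logistic and Cox.

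**Working it through.** The documents state no power, event count or expected result for these analyses, so there is no plan figure to reproduce. The check is a simulation of the written rule.

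**Inputs from the documents**

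- n = 120, 60 per arm (SAP 10).
- Mortality 25% to 40% (Protocol 3.7.1), so 0.25 × 120 = 30 to 0.40 × 120 = 48 deaths.
- "All statistical tests will be two-sided and will be performed at the 5% level of significance, unless otherwise stated" (SAP 12.5).
- Imbalance threshold p<0.20, borrowed from SAP 12.6 and 12.8, because 12.7.5 and 12.7.9 give none.

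**Inputs assumed, not in the documents**

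- Correlation r of the marker with severity: 0.3, 0.5, 0.7.
- Odds ratio (OR) for death per SD of severity: 1.5, 2.0, 2.5.
- Correlation of 0.3 between severity and the variable behind the P/F stratum, with half the patients in each stratum.
- Trauma omitted, since no prevalence is given.
- Logistic model.

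**Method.** Death depends on severity S only: logit P(death) = a + log(OR) × S. The marker is M = r × S + √(1 − r²) × noise, so it has no independent effect. Each of 3,000 trials per setting was analysed in two ways:

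- *Imbalance rule:* marker + P/F stratum + arm, with S added only if its t-test between arms gives p<0.20.
- *Fixed model:* the same, with S always included.

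**How often severity gets in.** Under randomization a p-value falls below 0.20 in 20% of trials, whatever the variable's link to death. The simulation gave 19% to 22%.

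**Percentage of trials in which the marker is significant** (imbalance rule / fixed model)

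| Mortality | OR per SD | r = 0.3 | r = 0.5 | r = 0.7 |
|---|---|---|---|---|
| 25% | 1.5 | 7.6 / 5.5 | 11.8 / 5.0 | 18.8 / 4.6 |
| 25% | 2.0 | 11.8 / 5.1 | 24.6 / 5.1 | 42.2 / 4.4 |
| 25% | 2.5 | 15.8 / 4.6 | 35.5 / 4.8 | 57.8 / 4.5 |
| 40% | 1.5 | 8.6 / 4.9 | 14.3 / 4.9 | 22.7 / 5.2 |
| 40% | 2.0 | 12.1 / 5.0 | 29.4 / 4.9 | 49.5 / 5.2 |
| 40% | 2.5 | 17.1 / 4.5 | 41.4 / 5.7 | 66.4 / 4.6 |

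The Monte Carlo standard error at 5% is √(0.05 × 0.95 / 3000) = 0.4 percentage points, so the fixed-model figures are consistent with 5%.

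**Cross-check of the middle case** (25% mortality, OR 2.0, r = 0.5). With severity never included the rate is 29.8%; always included, 5.1%. A rule that includes it one time in five should give about 0.8 × 29.8 + 0.2 × 5.1 = 24.9%. The simulation gave 24.6%. The P/F stratum was in every model and did not remove the inflation.

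**Youden cutoff.** Assume normal marker distributions, a true AUC of 0.60, 40 deaths and 80 survivors. The apparent index at the cutoff chosen in the same data averages about 0.23, while the true index at that cutoff is about 0.12. With an AUC of 0.50 the apparent index still averages about 0.11, against a true value of 0.

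**The case against.** The strongest answer is SAP 12.8. A reader of 12.7.5 and 12.7.9 might infer that the SAP as a whole admits APACHE III only by chance. The documents do not support that. The p<0.20 condition in 12.8 may attach only to the baseline measures named after APACHE III. If so, and if 12.8 governs the marker models, the fixed-model figures apply and the inflation disappears. But the grammar allows either reading, 12.8 does not name the marker models, and those sections carry their own lists. What stands is an ambiguity that decides the result.

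Other stronger readings also fail:

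- *All covariates are chosen by imbalance.* No. The P/F stratum (itself a severity measure), treatment and, for NLR, trauma are fixed in advance.
- *Steroids and trauma are ignored.* Not across the SAP. 12.8 includes trauma in its general rule and lists pre-randomization steroids for separate stratified or adjusted analyses. Those are described as linear mixed models, which do not suit a death outcome.
- *A marker will be declared prognostic, with an inflated cutoff accuracy.* The SAP has no rule for declaring this, treats secondary endpoints as supportive and exploratory (12.5), and names no accuracy figure to report at the cutoff.

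The size of the inflation depends heavily on assumed values of r and OR. The simulation is logistic; a Cox model that omits severity has the same confounding path, but its size was not computed.

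**Conclusion.** The point holds in limited form. Imbalance between arms is the wrong criterion for choosing covariates in a test of added prognostic value, and the SAP does not settle whether APACHE III is in these models regardless. Read without 12.8, the rule gave 7.6% to 66.4% false positives across the 18 assumed settings, against 4.4% to 5.7% with severity always included. Every setting was inflated, but no single figure should be taken as this trial's error rate. Read with an unconditional 12.8, there is no such inflation. The missing trauma term in 12.7.9 and the mixed model label are drafting faults to correct at the same time. The analyses are exploratory, and neither the primary endpoint nor the treatment comparison is affected.

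**What to change.** In both 12.7.5 and 12.7.9:

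1. Replace the imbalance rule with one fixed reference model, the same for both markers: baseline APACHE III, P/F stratum and treatment, with trauma either in both or in neither. Age needs no separate term, because APACHE III already contains an age score (SAP 8.2).
2. Name one model type, logistic or Cox.
3. Add the marker as a continuous term (log scale if skewed) and test it by likelihood ratio against the reference model.
4. State that this list overrides 12.8.
5. Make adjustment for pre-randomization steroids a sensitivity analysis for NLR.
6. If a Youden cutoff is reported, give its accuracy with optimism correction, for example by bootstrap.

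The cost is SAP wording; APACHE III is already required before randomization. The limit is events. With 30 to 48 deaths, four terms including the marker give 30/4 = 7.5 to 48/4 = 12 deaths per term; adding trauma gives 30/5 = 6 to 48/5 = 9.6. Neutrophil count, lymphocyte count and fibrinogen are collected only when available (Protocol Appendix A, SAP Table 2), so usable deaths may be fewer, and fewer again in the COVID-19 subgroup. A longer covariate list is not affordable.
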